Our primary endpoint is a returned HPV self-sampler kit. We have several planned subgroup analysis to help us understand if our intervention was more effective among certain population sub-groups. We therefore propose to examine whether the intervention was more efficacious among women with lower levels of educational attainment and those who are uninsured/underinsured. We consider all these analysis to be hypothesis generating, rather than hypothesis testing, given limited power. We also plan to examine several secondary endpoints, including: a) Access to care (health insurance, having a usual source of care, and visit to provider in six months). These would be analyzed as binary variables and would help explore if HPV self-sampling led to a decrease in access. b) Cervical cancer knowledge to help determine study fidelity. This is a continuous variable based on summed number of correct answers. c) Knowledge of test results and, for those with an abnormal screen, the proportion of women in each group who received appropriate initial follow-up within 30 days of the abnormal screen d) Acceptability of screening delivery.

14) **Procedures Involved***

Determination of eligibility The CHWs will screen potential participants for eligibility by asking whether they are 1) Haitian, Hispanic or African American, 2) 30-65 years of age or older, 3) have not had a Pap smear in the past three years, 4) has not had a hysterectomy, 5) has not been enrolled in a similar study (e.g. SUCCESS), 6) is not pregnant, 7) will not move in the next 6 months. For those women who screen potentially eligible, the CHW will further describe the study. Potential participants will be told that we are conducting a research study to determine the best method to increase rates of cervical cancer screening among women in their community. They will be told that the study will involve a brief education session about cervical cancer prevention and treatment, as well as instructions on how to use the HPV self-sampler we will be providing them with.

- Women who decline participation: For women who are potentially eligible but were not interested in participating, the brief demographic information collected during the eligibility screen (age, ethnicity) will be kept without any identifiable information. This data will be used to compare responders versus non-responders.

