cancer. It will also be stressed to women that if they have not seen a doctor recently they will still need to see a provider to address other health issues, which may include a gynecologic exam. They will also be advised that if HPV obtained through self-sampling is positive, they will need follow-up medical care at our clinical sites. The participant will have the option of self-sampling at home or mailing the kit back.

Group 2: Intervention Group (Mail Self-Sampler Kit): Participants receive the kit via mail. The Study Manager mails the self-sampler kit to the participant. The CHW will also provide the participant with brief education via phone utilizing a short intervention/educational script. The participant will follow instructions on instruction sheet provided in the kit, and once self-sampling is completed, participant will mail the kit to UM/SCCC.

Report of HPV Lab Results

The Study Manager will receive test results from lab and provide information to CHWs. CHWs will call participants within 4-6 weeks to notify them of their test results when they are received. Participants who test negative will be encouraged to follow-up with their doctor and rescreen in 36 months, based on the US Preventive Services Task Force (USPSTF) guidelines. Participants whose test results indicate insufficient sample (insufficient cellular quantity for analysis) would be asked if they had a hysterectomy. If no, the participant will provide a second sample, and an appointment will be scheduled by CHW. If answered yes, the HPV lab result will be reported to the Study Manager. Participants who test positive for HPV will be navigated to appropriate follow-up care with our community partners and/or Jackson Memorial Hospital (JMH) within 30 days of receiving the result. JMH is the safety net hospital for Miami-Dade County and provides free and low cost care to indigent and medically underserved individuals in the Miami metropolitan area. The CHWs will work with JMH staff to ensure that women with abnormal findings receive timely follow up. The CHWs will follow up with participants who do not return the kit within 30 days.

At 4 months, the CHW calls participants in both arms to verify contact information only.

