Exit Survey at 6 months: The CHE will conduct an exit interview/ survey at 6 months with all who participated in the baseline procedures (Arms 1 and 2). The survey will take approximately 30 minutes. At exit, both arms will be offered the option of self-sampling at home or mailing the kit back. The participant on Arm 2 is offered the HPV self-sampler again to be done at home or the participant has the option of mailing it back, in case she did not have the opportunity to complete self-sampling. After completion of the intake survey, the participant will receive a \$25 gift card for their time and participation.

15) Data and Specimen Banking

. The Study Manager will take the specimens to the Oncogenomic Core Facility at UM Sylvester Comprehensive Cancer Center (SCCC) for high-risk HPV detection and HPV viral genotyping on a weekly basis. Specimens will be labeled with a number that matches the number assigned to the participant during the study intake. The specimens will be processed and Results will be reported back to Study Manager within 2 weeks, who will obtain signature from [name]. He will sign and date lab result sheet. Copies of results will be filed and kept in locked cabinet and uploaded to REDCap. The leftover samples will be banked in a secure freezer at the Sylvester

Comprehensive Cancer Center at the University of Miami, Miller School of Medicine for future analysis.

16) Data Management

All of the data collected via iPad or paper forms and supporting documentation will be uploaded and stored on REDCap, a web-based management application that is designed specifically for investigators and their research teams. It supports processes for participant recruitment, data collection, database management, reporting and study execution. A major strength for our proposal is that REDCap allows all study related information to be centralized yet be accessed through the internet from anywhere through encrypted and password protected access granted only to authorized UM personnel as designated by the study PIs. It is easy to use, reliable, fully HIPPA complaint and secure. A major advantage of using this system is that UM provides this important resource to UM and associates (such as non UM community research partners) at no cost. This includes technical support and effort of REDCap team staff who provide technical assistance to investigators.

17) **Risks to Subjects**

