Grant funding from the NIH enabled the creation of a University institute to address cancer health disparities. The institute, Jay Weiss Institute for Health Equity, previously known as **Sou**th Florida **C**enter for Reducing **C**ancer Disparities or SUCCESS, is focused on attenuating the excess burden of cervical cancer observed in Little Haiti, Hialeah, and West Perrine. For the past three years, the Jay Weiss team, comprised of diverse academic and community stakeholders, has been working to increase screening opportunity through outreach and education that reflects the unique cultural and linguistic needs of our target communities, and builds upon the assets of our extensive network of community partners. With the support and active participation of such partners, we have played a critical role in over 100 events held throughout Hialeah, Little Haiti, and West Perrine this year alone, and educated an estimated 5,474 people about cervical cancer and the importance of early detection of disease. This study provides an opportunity to extend our impact, and continue our work in our targeted communities.

22) Sharing of Results with Subjects

CHWs will notify participants of their test results when they are received. Participants who test negative will be encouraged to follow up with their doctor and rescreen in 36 months, based on the US Preventive Services Task Force (USPSTF) guidelines. Participants whose test results indicate insufficient sample would be asked if they had a hysterectomy. If no, the participant will provide a second sample, and an appointment will be booked by CHW. If answered yes, the HPV lab result will be reported to the Study Manager. Participants who test positive for high-risk strains of HPV will be navigated by the CHW to appropriate follow-up care with our community partners and/or Jackson Memorial Hospital (JMH) within 30 days of receiving the result. JMH is the safety net hospital for Miami-Dade County and provides free and low cost care to indigent and medically underserved individuals in the Miami metropolitan area. The CHWs will work with JMH staff to ensure that women with abnormal findings receive timely follow up. The CHWs will follow up with participants who do not return the kit within 30 days.

23) Setting

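### The SAP's paired McNemar test cannot analyse the 30-day follow-up endpoint, which is a between-arm proportion; the endpoint's start date is also undefined

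*Protocol*

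**What the plan says.** Protocol section 13 lists, under secondary endpoint (c), knowledge of test results and, for women with an abnormal screen, "the proportion of women in each group who received appropriate initial follow-up within 30 days of the abnormal screen". It does not say which date counts as the date of the abnormal screen.

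The SAP (Statistical Analysis) has one sentence on secondary outcomes: paired McNemar chi-square tests, on the whole sample and again within each neighborhood site. Its between-arm chi-square tests are for baseline characteristics and for the proportion screened. Its logistic models are for screening completion.

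Protocol section 14 (Report of HPV Lab Results) covers the handling of results in three steps:

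- Who gets results from the laboratory: "The Study Manager will receive test results from lab and provide information to CHWs".
- The time limit for telling women: "CHWs will call participants within 4-6 weeks to notify them of their test results when they are received".
- Care after a positive result: "Participants who test positive for HPV will be navigated to appropriate follow-up care with our community partners". The safety-net hospital is named as another route, and the limit is "within 30 days of receiving the result".

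Section 22 repeats the procedure but gives no number of weeks for the call: "CHWs will notify participants of their test results when they are received". Positive women again "will be navigated by the CHW to appropriate follow-up care", with the same 30-day limit. Section 15 says specimens go to the laboratory "for high-risk HPV detection and HPV viral genotyping on a weekly basis", and results return to the Study Manager within two weeks.

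**The concern.** The endpoint asks whether timely follow-up differs between women given the kit by a community health worker (CHW) and women sent it by mail. A test that pairs each woman with herself and pools the arms does not address that question. If the SAP is followed literally, the analyst has no valid procedure for (c). The method would then be chosen after the data are seen, or the comparison would be dropped.

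The undefined start date matters for scoring. Two analysts could date the window differently and classify the same late-notified woman differently. Only women with an abnormal result are involved.

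**Working it through.** The plan gives no sample size, power or event count for this endpoint, so there is no figure to reproduce. The check has three parts.

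**1. Structure of the endpoint against structure of the test**

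| | Endpoint (c) | Paired McNemar |
|---|---|---|
| Values per unit | one, after the screen | two linked binary values |
| Groups | two independent randomized arms | none; one set of pairs |
| Population | women with an abnormal screen | whole sample, and by site |
| Quantity | difference between arms in a proportion | change within pairs |

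McNemar's statistic is (b − c)² / (b + c), where b and c count pairs that change in each direction.

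- Pairing within a woman: follow-up of an abnormal screen has no value before that screen, so b and c do not exist. If every baseline value were set to *no*, then c = 0 and the statistic reduces to b, the number of women followed up. That would test whether anyone was followed up, and arm would not enter.
- Pairing across arms: Protocol section 14 (Randomization) gives each woman the next value in an allocation table. No matching is described, so there are no pairs between arms.

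The stated test therefore cannot produce the comparison in section 13.

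**2. Likely size of the subset (illustration on assumed inputs)**

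Assume equal allocation of the 700 women, 350 per arm; kit return of 60% to 95%; and an abnormal result in 10% to 20% of returned kits. The documents give none of these assumed values.

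- Lowest: 350 × 0.60 × 0.10 = 21 per arm.
- Highest: 350 × 0.95 × 0.20 = 66.5, about 66 per arm.

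For follow-up of 80% against 60% (also assumed), two-sided 0.05, the normal approximation is power = Φ{[0.20 − 1.96·√(2 × 0.7 × 0.3 / n)] / √[(0.8 × 0.2 + 0.6 × 0.4) / n]}. It gives 0.29 at n = 21 and 0.72 at n = 66.5. The comparison is likely to be imprecise, and small cells are possible.

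**3. The start date**

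Inputs: window 30 days (sections 13, 14 and 22); call limit of 4 to 6 weeks, 28 to 42 days (section 14, start not stated); result received on day r after collection, at most 7 + 14 = 21 (section 15, weekly transport plus two weeks). Mail time is not given and is taken as 0; each mail day adds one to r.

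- *Window and call limit both from the result:* days left = 30 − call day. At week 4, 30 − 28 = 2. At week 6, 30 − 42 = −12.
- *Window from the result, call limit from collection:* the window closes on day r + 30. Left at week 4 = r + 30 − 28 = r + 2, never below 2. Left at week 6 = r + 30 − 42 = r − 12, which is −5 at r = 7, 0 at r = 12, 2 at r = 14 and 9 at r = 21. The overrun occurs only if the result is back before day 12.
- *Window from the woman's own receipt of the result:* it opens when she is told, so all 30 days remain whatever the call date.

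**The case against.** **On the test.** The McNemar sentence may have been meant only for binary items asked at both interviews, such as access to care, where a paired test of change is reasonable. That is a fair reading of intent, but the SAP does not limit the sentence, and on this reading (c) has no named test. The gap stands either way.

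**On timing.** A reader might infer that the two limits in section 14 contradict each other. The documents do not support that. The subject of the 30-day sentence is the participant, so receiving the result can mean her own receipt, which leaves no conflict. Section 14 also uses the verb for the Study Manager, so the text does not settle it. The start of the 4 to 6 weeks is not stated, and a limit of that length fits total turnaround from sampling, where overruns are confined to early results. Two upper limits that can both be met by calling sooner are not contradictory, and sections 14 and 22 both speak of notifying women when results are received. This objection largely succeeds; what remains of the timing point is an undefined date.

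Dating the window from collection would be harsher: it would close on day 30, while navigation within 30 days of a day-21 result could run to day 51. That reading is the less natural one, because a screen is not known to be abnormal until the result exists.

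**On the event.** A reader might also infer that *received* in section 13 and *navigated* in sections 14 and 22 set up two scoring rules. They do not. Section 13 is the only scoring text; the other two describe what CHWs do. A woman navigated but not yet seen has not received follow-up.

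**Conclusion.** The test for endpoint (c) is wrong as written: a paired test on pooled arms cannot compare one post-screen proportion between independent arms. This needs no numerical assumption and does not depend on the timing question.

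The start date is a secondary, smaller point. A call at six weeks falls 12 days after the window if both clocks run from the result, falls after it only for results back before day 12 if the call limit runs from collection, and causes no conflict if the window runs from the woman's own receipt. The documents do not show how many women would be called that late, and they set no result-call rule that differs by arm, so bias between arms should not be inferred.

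The effect is limited to one part of one secondary endpoint, among women with an abnormal result. The primary endpoint, a returned kit, is unaffected.

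**What to change.** In the SAP:

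- Limit McNemar to binary items measured at both interviews.
- For (c), name a two-group comparison by arm among women with an abnormal result: chi-square, or Fisher's exact test if counts are small. Give the numerator and denominator in each arm.
- State that this subset is defined after randomization, by returning a kit and having an abnormal result, and is likely small. Kit return is itself the primary endpoint, so the two subsets may differ for reasons other than chance, and the comparison should be read with that in mind.

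In the protocol, reconcile sections 13, 14 and 22 on the date that starts the 30 days, say when the 4 to 6 weeks start, and carry the same scoring date into the SAP. Which date to use is for the investigators. No change to the care timeline is proposed.

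The cost is a few sentences. The test change needs only arm and follow-up status. If the Study Manager's receipt date is chosen, one date field may be needed: the protocol does not say that date is recorded, and the dated signature in section 15 comes after receipt. With that choice, mail, transport and laboratory time before receipt would not be reflected in the endpoint. No visits are added.

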Protocol Title: Addressing Cervical Cancer Disparity in South Florida: CBPR in Action Version Date: 2/4/16 NCT#02202109

- 1) **Protocol Title** Addressing Cervical Cancer Disparity in South Florida: CBPR in Action
- 2) **Principal Investigator** [name], MPH
- 3) **Sub-investigator** [name], MPH
- 4) **Study Contact** [name], MBA
- 5) Study Personnel (Listed on IRB7)
- 6) **IRB Review History**

N/A

7) **Objectives**

The study entitled "Health in Your Hands" will test the significance of community health worker participation by comparing Human Papilloma Virus (HPV) self-sampling provided by a community health worker and HPV self-sampling provided by mail. The study will enroll 700 participants in communities characterized by health disparities and lack of access to the formal healthcare system, such as Little Haiti, Hialeah, and South Dade.

8) Background*

In Miami, Florida, cervical cancer is a particular problem for Haitian and Caribbean Hispanic women. When compared to other racial/ethnic minority and immigrant groups in the Miami metropolitan area, Haitian and Hispanic women contribute disproportionately to cervical cancer incidence, morbidity and mortality, largely as a function of their underutilization of Pap smear screening. They do not undergo Pap smear screening for a myriad of reasons, including, but not limited to: poverty; language difficulties; limited access to health care; lack of knowledge about cancer and the importance of early detection; cancer fatalism or the belief that cancer implies death; and, cultural norms about health and disease prevention. The proposed project aims to overcome such barriers.

With funding from the National Cancer Institute, we have documented the prevalence of lifetime and routine Pap smear among women living in our communities of interest. Between March and May 2011, the community health workers approached approximately 200 women from various community venues across Little Haiti, Hialeah and West Perrine including Laundromats, health clinics, and churches. Of the participants, 71% reported having at least one Pap smear in their life. Of those with a history of screening (n=143), only 80% reported having a least one Pap smear in the past three years as recommended by national guidelines. There is not a direct comparison for our data, though in relation to national averages and data, the women in our sample appear to be under-screened.

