Protocol Title: Addressing Cervical Cancer Disparity in South Florida: CBPR in Action Version Date: 2/2/17 NCT#02202109

Statistical Analysis

Baseline characteristics were compared across the two study arms using chi-square tests (categorical data) and t-tests (continuous data). Crude differences in proportion of women screened by study arm (overall and stratified by neighborhood site) were tested using chi-square tests. We then modeled the association between sociodemographic variables and screening completion using univariate and multivariable logistic regression analyses. We included neighborhood site, age, income, insurance status, education, Pap history, marital status and citizenship status as covariates in the multivariable analysis. Race/ethnicity was not analyzed as it was highly collinear with site (e.g. all Haitians resided in Little Haiti). We report odds ratios (ORs) and corresponding 95% confidence intervals (CI) for the regression analyses. Secondary outcomes were analyzed using paired McNemar chi-square tests for the overall sample, and stratified by neighborhood site. All statistical tests were two-sided, with significance set at the p < 0.05 level. The data were analyzed using SAS 9.4 (SAS Institute Inc., Cary, NC, USA).

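### The SAP's paired McNemar rule for secondary outcomes cannot give the by-arm follow-up proportion that Section 13(c) of the protocol asks for

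*Protocol*

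**What the plan says.** Protocol Section 13 (Study Endpoints) names the primary endpoint: "Our primary endpoint is a returned HPV self-sampler kit". Item (c) of the secondary endpoints covers knowledge of test results and, for women with an abnormal screen, "the proportion of women in each group who received appropriate initial follow-up within 30 days of the abnormal screen". This fixes a denominator (women with an abnormal screen) and asks for the result by group.

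The SAP has one sentence on secondary outcomes: "Secondary outcomes were analyzed using paired McNemar chi-square tests for the overall sample, and stratified by neighborhood site". Study arm does not appear in it. The SAP compares baseline characteristics between the arms, but its only between-arm test of an outcome concerns screening: "Crude differences in proportion of women screened by study arm (overall and stratified by neighborhood site) were tested using chi-square tests". The logistic models also have screening completion as their outcome.

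On timing, Section 14 (Report of HPV Lab Results) says that women who test positive "will be navigated to appropriate follow-up care with our community partners and/or Jackson Memorial Hospital (JMH) within 30 days of receiving the result", and Section 22 repeats that period.

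**The concern.** Whether women with an abnormal result reach care in each arm is a natural companion to the primary question, since a delivery method that brings in more kits is of less use if positive results are not acted on. Section 13(c) is where the protocol asks this, and the SAP's analysis rule does not fit it. McNemar's test compares two linked binary measurements on the same woman. Here there is one measurement per woman, and the contrast of interest lies between two independent groups.

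The likely result is that the by-arm figure is left out, or that an analysis is chosen after the data are seen. An unpaired comparison also needs a caution. A study HPV result requires a returned sample, and kit return is what the arms are meant to influence. The women compared are therefore selected after randomisation.

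**Working it through.** The documents give no return, positivity or follow-up rates and no allocation ratio, so there is no planned figure to reproduce. All rates below are assumptions. The 350 per arm assumes 1:1 allocation of the total in Section 7 ("The study will enroll 700 participants").

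**1. What the stated test can see.** McNemar's statistic is (b − c)²/(b + c), where b and c count women who change in each direction between two linked measurements. For 13(c) there is no earlier measurement, so b and c cannot be formed. Even for an item asked at intake and exit, arm does not enter the formula. Two sets of invented counts show this:

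- One arm has b = 60, c = 20 and the other b = 20, c = 60. Each arm alone gives 40²/80 = 20.0, in opposite directions. Pooled: (80 − 80)²/160 = 0, p = 1.0.
- Both arms have b = 60, c = 20. Pooled: (120 − 40)²/160 = 40.0, although the arms do not differ.

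Stratifying by neighborhood site repeats this within each site and still does not compare arms.

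**2. Precision of an unpaired comparison.** Half-width of the 95% interval = 1.96 × √(2 × p(1 − p)/n), with p = 0.70 followed up in both arms.

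| Return | Positive | Abnormal screens per arm | Half-width |
|---|---|---|---|
| 60% | 10% | 350 × 0.6 × 0.1 = 21 | 1.96 × √(0.42/21) = 0.277 |
| 90% | 20% | 350 × 0.9 × 0.2 = 63 | 1.96 × √(0.42/63) = 0.160 |

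**3. Selection through kit return.** Suppose that 70% return in both arms, with 80% follow-up among those who screen abnormal. In one arm a further fraction g also return, with follow-up e, and positivity is equal throughout. With no effect of arm on any woman's follow-up, the subset difference is (0.70 × 0.80 + g × e)/(0.70 + g) − 0.80:

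- g = 0.05, e = 0.60: 0.59/0.75 − 0.80 = −1.3 points
- g = 0.15, e = 0.40: 0.62/0.85 − 0.80 = −7.1 points
- g = 0.20, e = 0.20: 0.60/0.90 − 0.80 = −13.3 points
- e = 0.80, any g: 0

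**4. Proportion returned, positive and followed up among all randomised.** Under the rates in step 2:

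- Low end: 0.6 × 0.1 × 0.7 = 4.2%, or 14.7 of 350; half-width 1.96 × √(2 × 0.042 × 0.958/350) = 3.0 points.
- High end: 0.9 × 0.2 × 0.7 = 12.6%, or 44.1 of 350; half-width 1.96 × √(2 × 0.126 × 0.874/350) = 4.9 points.

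**5. The 30-day interval, passages side by side.** Section 13(c) counts from the abnormal screen and ties it to no date. Sections 14 and 22 count from receipt of the result and do not say who receives it. Section 14 puts the call to the participant at 4 to 6 weeks (28 to 42 days), with no stated start. Under Section 15, specimens go to the laboratory "for high-risk HPV detection and HPV viral genotyping on a weekly basis" and results come back within 2 weeks. That is up to 7 + 14 = 21 days from receipt of the sample, or 14 if the two weeks include the wait. The possible start events can therefore lie weeks apart, or they may be one and the same.

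**The case against.** The strongest reply is that McNemar was meant for items asked at intake and exit, such as access to care, and that nobody would apply it to 13(c). That is plausible, though the SAP does not say so. It moves the gap without closing it, because 13(c) is then left with no analysis at all.

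A second reply is that 13(c) asks only for a proportion in each group and names no test, so two reported percentages would satisfy it. This stands: a formal test is not promised, and the fix below is mainly a reporting line. But the SAP does not provide for by-arm percentages either.

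A third is that any endpoint limited to women with an abnormal screen depends on who was screened, and that Section 13 states the denominator openly. This also stands, and the remedy is a caution beside the estimate. The link to kit return is itself partly an inference: the protocol does not define an abnormal screen, and the kit carries information on scheduling a Pap smear, so a Pap result is not expressly excluded.

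Finally, the protocol does not define appropriate follow-up, and it describes the women concerned as HPV-positive in Section 14 but as positive for high-risk strains in Section 22. Correcting the test does not by itself make the endpoint scoreable.

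**Conclusion.** The mismatch holds on the text alone and needs no assumption: the stated rule cannot deliver the by-arm follow-up proportion. It affects one part of one secondary endpoint and leaves the primary analysis as it is. The expected imprecision, a half-width of about 16 to 28 points, depends on the assumed rates in the working.

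A reader might infer four stronger points, which the documents do not support:

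- That the SAP never compares the arms. It does so for baseline characteristics and for screening.
- That McNemar would produce a falsely significant result for 13(c). This requires an invented baseline value for every woman.
- That the subset comparison is biased. The 0 to 13 points shown rest wholly on assumed rates, and the range includes zero.
- That the 30-day passages contradict each other. Sections 14 and 22 set a care target and score no endpoint. If the two phrases mean the same event there is no conflict, and the number of women affected may be zero. This is a note for reconciliation only.

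**What to change.** In the SAP, exempt this endpoint from the McNemar rule. Report the follow-up proportion by arm among women with an abnormal screen, with the unpaired between-arm difference and its 95% confidence interval. If a test is given, use an exact one where counts are small. State that the subset is defined after randomisation, so the comparison is descriptive and not protected by randomisation.

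Optionally, add by arm the proportion returned, positive and followed up among all randomised women. It keeps the randomised denominator but mixes kit return with follow-up and rests on about 15 to 44 events per arm under the assumptions above. It should sit beside the subset figure and not replace it.

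Separately, reconcile Section 13(c) with Sections 14 and 22, and with the timing of the participant call in Section 14, so that one stated start event is applied identically in both arms. This review does not choose the event or the time limit.

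The cost is an SAP sentence, a table row or two, and a definition. The main downside is the imprecision. Because the SAP is written in the past tense, the change should be dated and marked as added at that stage, and some result and follow-up dates may have to be abstracted retrospectively.
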